12.2 Null and Alternative Hypotheses

The null hypothesis: there is no difference in the mean CTC levels over time among patients exposed to volatile anesthesia compared to patients in the control group (propofol anesthesia).

The alternative hypothesis: there is a difference in the mean CTC levels over time among patients exposed to volatile anesthesia compared to patients in the control group (propofol anesthesia).

The primary objective of this study is to reject the null hypothesis H_0 .

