Objective(s)/ Outcome(s):	> Primary outcome: to determine if there is a difference in the mean of blood CTC levels over time among patients exposed to volatile anesthetics (i.e. receiving sevoflurane) compared to patients in the control group (i.e. receiving intravenous anesthesia with propofol) > Secondary outcomes: A) to determine if anesthesia interferes with the number and activity of blood natural killer (NK) cells

	B) to examine if CTC levels correlates with the presence of extracapsular spread of tumor cells (ECS) in the histopathological findings in axillary lymph nodes
Number of Subjects:	Total number of 232 patients.
Diagnosis and Main Inclusion Criteria:	
Diagnosis: primary breast cancer
 
Inclusion Criteria:
 
 > Female > Age 18 to 85 > ASA I-III > Primary breast cancer (TNM stage = T1-3, N0-2, M0) > Primary surgery > Written informed consent
Main Exclusion Criteria:	
 > Metastatic breast cancer > Other than primary surgery (recurrence, reconstruction) > Pre-operative chemotherapy or radiotherapy > Auto-immune disease, HIV, other active cancer, age>85, ASA IV or V > Concomitant regional anesthesia > Chronic opioids medication > Any systemic immunosuppressive therapy > Known hypersensitivity or suspected allergy to propofol, soya or egg proteins > Known hypersensitivity to volatile anesthetics (malignant hyperthermia) > Pregnancy > Breast feeding > Non German-speaking patients > Enrollment in any other clinical trial during the course of this trial, 30 days prior to its beginning or 30 days after its completion
Study Product, Dose, Route, Regimen:	Sevoflurane will be used in its inhalational form via an endotracheal tube for maintenance of anesthesia. The dose and regimen will be adjusted to keep an adequate depth of anesthesia (MAC 0.8-1.2), according to BIS values between 40 and 60
Duration of administration:	Administration will be limited to the length of the surgical procedure
Reference therapy, Dose, Route, Regimen:	Propofol will be intravenously administered via a target-controlled infusion (TCI) device providing a drug dose ranging from 3.0 to 5.0 mcg/ml. The dose and regimen will be adjusted to keep an adequate depth of anesthesia, attested by BIS values between 40 and 60.
Study Schedule:	March 2014 to July 2018

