
Statistical Methodology:
	
Primary analysis : the number of CTC in peripheral blood will be measured before and after exposition to general anesthesia using a linear mixed model with random effects matrix, which accounts for within-subject treatment factor (i.e. anesthesia regimen)
 
Secondary analyses: since most reports refer to CTC levels as a binary outcome (i.e. positive versus negative endpoints using a cut-off value of $\geq 5\text{CTC}/7.5\text{ ml blood}$), data transformation from continuous into a binary variable will be performed using the same cut-off value. This new data set will be analyzed using a logistic regression mixed model with random effects matrix.
 
All primary and secondary analyses will be performed following an intention-to-treat (IIT) model. This analysis will subsequently compared to a per-protocol analysis to ensure stability of results. Results will be reported as OR, 95% confidence intervals and their associated p-values. A p-value < 0.05 will be considered statistically significant

GCP Statement:
	
This study will be conducted in compliance with the protocol, the current version of the Declaration of Helsinki, and ICH-GCP as well as all national legal and regulatory requirements.

STUDY SCHEDULE

Study Periods	Screening	Treatment Period		Follow-up	
Visit	1	2	3	4	5
Postoperative day	-1	0a	0b	2	3
Medical history	x				
Physical Examination	x				
Vital signs		x	x	x	x
Concomitant therapy	x	x	x	x	x
In-/Exclusion Criteria	x				
Subject information and informed consent	x				
Pregnancy test	x				
Randomization		x			
Study medication (sevoflurane or propofol)			x		
1° variable: CTC level		x	x	x	x
2° variable A		x	x	x	x
2° variable B*			x		
2° variable C					
Perioperative data	x	x	x	x	x
Safety variables: AE			x	x	x

Visit 1: 24h before surgery

Visit 2 (0a): before induction of anesthesia

Visit 3 (0b): end of surgery, before extubation

Visit 4: 48h after surgery

Visit 5: 72h postoperative, before hospital discharge

Primary variable: assessment of circulating tumor cells in peripheral blood

Secondary variable A: assessment of natural killer (NK) cells (number and activity)

Secondary variable B: extracapsular tumor spread in axillary nodes

* Data will be collected after completion of the study

Perioperative data: demographics and confounding factors

TABLE OF CONTENTS

1.	LIST OF ABBREVIATIONS AND DEFINITIONS OF TERMS	8

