5. STUDY OBJECTIVES AND OUTCOMES

We will conduct a prospective, randomized, double blinded, controlled study over a 52-month period to investigate whether commonly used anesthetics (volatile *versus* intravenous) affect the level of circulating tumor cells in patients undergoing surgery for primary breast cancer.

Hence, the **primary objective** is to compare the effects of 2 anesthetic regimens (sevoflurane *versus* propofol) on perioperative CTC levels measured at 4 different time points. Blood levels (i.e. number) of CTC will be determined using the CellSearch® approach, as described below.

Two **secondary objectives** will be determined:

A) To determine if anesthesia interferes with NK cells by measuring NK cells number and activity at 4 different time points;

B) To establish if the level of CTC correlates with the presence of ECS in the histopathological findings of axillary lymph nodes (exclusively in patients undergoing breast surgery with axillary dissection).

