6. STUDY DESIGN

6.1 General Design

We will conduct a prospective, randomized, double blinded, controlled study over a period of 52 months. We will consider adult female patients undergoing surgery for primary breast cancer. Expecting a dropout rate of 10% over time, we will recruit a total of 232 patients (i.e. 116 in each study group).

Patients will be screened for eligibility according to the inclusion and exclusion criteria on the day prior to surgery. Written informed consent will be subsequently obtained. A pregnancy test will be performed for all included patients.

On the day of operation, the patients will be premedicated with midazolam *per os* (3.75mg to 7.5mg). Randomization will be performed according to a computer-generated anesthesia-assignment (www.randomizer.at) once the patient will be installed for induction of anesthesia. By this means, concealment of random allocation will be ensured.

After preoxygenation, induction of anesthesia will be administrated in both groups similarly, using fentanyl 2-3mcg/kg, Pentothal 4-6 mg/kg and rocuronium 0.6mg/kg intravenously. Maintenance of anesthesia will be conducted following the assignment group:

1) in “Group Sevo”, anesthesia will be maintained with sevoflurane in 80% oxygen, adjusted to keep an adequate depth of anesthesia (minimal alveolar concentration (MAC) between 0.8 and 1.2), attested by bispectral (BIS) index values between 40 and 60.

2) in “Group Propofol” anesthesia will be maintained with a target-controlled infusion (TCI) device providing an intravenous propofol dose adjusted to keep an adequate depth of anesthesia (TCI values: start after induction with 2.0mcg/ml, then ranging from 3.0mcg/ml to 5.0mcg/ml), attested by BIS index values between 40 and 60.

Patients will be ventilated with 80% oxygen in air.

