6.2 Primary Study Endpoint: blood CTC levels

The primary endpoint, blood CTC levels, will be assessed at 4 pre-defined time points using the CellSearch® approach: two 7.5ml samples of blood will be collected pre-operatively (visit 2, before induction of anesthesia), at the end of surgery (visit 3, before extubation) and two times postoperatively (visit 4, 48h postoperative, and visit 5, 72h after surgery, before hospital discharge). The number of CTC per 7.5ml of peripheral blood will be determined by the CellSearch® system within 96 hours of blood collection. The analysis will account for the effect of repeated measurements over time (within-subject factor) and the effect of anesthesia regimen (between-subject factor) as described under section 12.

The CellSearch® approach

The CellSearch® assay contains a ferro fluid-based capture reagent and immunofluorescent reagents. The ferrofluid reagent consists of particles with a magnetic core surrounded by a polymeric layer coated with antibodies targeting the epithelial cell adhesion molecule (EpCAM) antigen for capturing CTC. After immunomagnetic capture and enrichment, fluorescent reagents (anti-CK-phycoerythrin, DAPI, and anti-CD45-allophycocyanin) are added for identification and enumeration of CTC. (www.veridex.com)

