6.4.3 Visit 3 (day of surgery – end of surgery, before extubation)

- Maintenance of anesthesia following the assignment group (sevoflurane or propofol)
- Vital signs will be recorded, concomitant therapy* will be administered
- 2x7.5ml + 2x8ml of blood will be collected and sent for CTC/NK cells assessment (1° variable and 2° variable A)
- Histopathological findings (2° variable B): data related to this endpoint will be collected after completion of the study.
- Perioperative data collection as listed in Table 3
- AE or SAE will be recorded

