12. STATISTICS

12.1 Statistical and Analytical Plans

This is a multicentric randomized controlled trial comparing the effect of 2 different anesthetic regimens (sevoflurane *versus* propofol) on perioperative levels of CTC in patients undergoing surgery for primary breast cancer.

Using a strict 4 time-points schedule, the number of CTC in peripheral blood will be measured before and after exposition to general anesthesia (primary outcome).

Using a mixed model analysis, the effect of two independent variables on the mean level of CTC will be explored: a within-subject time factor (i.e. variation of CTC levels over time) and a between-subject treatment factor (i.e. anesthesia regimen).

Fixed randomization based on a 1:1 allocation ratio will be performed using minimization (www.randomizer.at). Patients will be stratified according to their ASA class during the randomization process, which will be performed using a web-based interactive allocation platform (www.randomizer.at).

Accordingly, the risk of allocation and selection bias will be negligible. Restriction and stratified randomization are likely to minimize the risk of unbalanced known and unknown confounders. Blinding of participants and outcome assessors (laboratory staff, pathologist) will prevent measurement/detection bias.

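### The pre-induction CTC sample is counted as one of four primary-outcome time points and given no baseline role, which costs power if the test is the four-visit regimen effect; 12.5 does not say which contrast the 0.3 and the 116 refer to

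*Protocol*

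**What the plan says.** **Hypothesis.** The synopsis gives the primary outcome as "to determine if there is a difference in the mean of blood CTC levels over time among patients exposed to volatile anesthetics" against propofol. Section 12.2 words the null in the same terms: "there is no difference in the mean CTC levels over time among patients exposed to volatile anesthesia".

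**Time points.** Section 5 sets the objective as the effect of the two regimens "on perioperative CTC levels measured at 4 different time points". Section 6.2 lists these as visit 2 (before induction), visit 3 (end of surgery, before extubation), visit 4 (48 h) and visit 5 (72 h). Section 12.1 repeats the scheme: "Using a strict 4 time-points schedule, the number of CTC in peripheral blood will be measured before and after exposition to general anesthesia".

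**Model.** Sections 12.1 and 12.3.1 specify a linear mixed model with a within-subject time factor and a between-subject regimen factor. The synopsis likewise says that CTC "will be measured before and after exposition to general anesthesia using a linear mixed model". No section makes visit 2 a covariate, a constrained baseline or the reference for change. None says whether the test is the regimen main effect, the regimen-by-time interaction or a contrast at named visits.

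**Exposure.** Section 6.1 states that "induction of anesthesia will be administrated in both groups similarly". The assigned drug enters at maintenance, which section 6.4.3 lists under visit 3.

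**Sample size.** Section 12.5 uses an effect size of 0.3 (also called a 30% difference), a within-subject correlation of 0.4, 80% power, two-sided 5% and 10% dropout over time. It arrives at 116 per group and ties the 0.3 to no visit or contrast.

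**The concern.** Visit 2 precedes any difference in treatment, so the expected between-arm difference there is zero by design. Averaging it in as a fourth outcome adds chance variation and no treatment effect. Used as a baseline, the same measurement would remove between-patient variation from the later visits.

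At stake are efficiency and the meaning of the power statement. Whether the stated 80% applies to the hypothesis in 12.2 depends on which contrast the 0.3 describes and which contrast is tested, and the protocol fixes neither. Settling this in advance also closes off a choice between main effect and interaction once data are seen.

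**Working it through.** **Inputs from 12.5:** effect 0.3 (read as SD units), correlation 0.4, power 80%, two-sided 5%, 10% dropout, 116 per group. **Assumptions of this check:** normal theory, equal variance (SD 1) at each visit, and the 0.4 taken as compound symmetry (every pair of visits correlated 0.4). The protocol states no structure.

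**Formulas.** Patients per arm: n = 2(1.96 + 0.8416)² V/δ² = 15.70 V/δ². Power: Φ(δ/√(2V/n) − 1.96). V is the variance factor of the contrast:
- four-visit mean: V = (1 + 3×0.4)/4 = 0.550
- visit 3-5 mean: V = (1 + 2×0.4)/3 = 0.600
- visit 3-5 mean adjusted for visit 2: V = 0.600 − 0.4² = 0.440

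**1. The plan's own figure.** Three measurements, δ = 0.3: 15.70×0.600/0.09 = 104.65, and 104.65/0.9 = 116.3, which matches 116. Four measurements: 15.70×0.550/0.09 = 95.9, and 95.9/0.9 = 106.6, which does not.

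**2. Relative efficiency.** With zero effect at visit 2 and an equal effect at visits 3 to 5, the four-visit mean carries 3/4 of the effect. The ratio of patients needed is (0.550/0.75²)/0.440 = 0.978/0.440 = 2.22, whatever the size of the effect. Under other assumed structures:
- AR(1) at 0.4: (0.448/0.5625)/0.503 = 1.58
- correlation of visit 2 with later visits 0.2: (0.475/0.5625)/0.560 = 1.51
- correlation of visit 2 with later visits 0: (0.400/0.5625)/0.600 = 1.19

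**3. Power with 104 completers per arm (116×0.9), compound symmetry.** Worked for 0.3 at each of visits 3 to 5:
- four-visit mean: δ = 0.225, 0.225/√(2×0.550/104) = 2.188, Φ(0.228) = 59%
- unadjusted visit 3-5 mean: 0.3/√(2×0.600/104) = 2.793, Φ(0.833) = 80%
- adjusted visit 3-5 mean: 0.3/√(2×0.440/104) = 3.261, Φ(1.301) = 90%
- treatment-by-time, 3 df: noncentrality (104/2)×(0.225² + 3×0.075²)/0.6 = 5.85, power 51%

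| True difference at visits 2/3/4/5 (SD) | Four-visit mean | Treatment-by-time | Visit 3-5 mean | Adjusted visit 3-5 mean |
|---|---|---|---|---|
| 0/0.3/0.3/0.3 | 59% | 51% | 80% | 90% |
| 0/0.4/0.4/0.4 (four-visit difference = 0.3) | 83% | 78% | 96% | 99% |
| 0/0.3/0/0 | 11% | 51% | 15% | 19% |

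For the first row, AR(1) gives 68% for the four-visit mean and 86% for the adjusted mean. A correlation of 0.2 between visit 2 and later visits gives 65% and 82%.

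**4. Patients per arm for 80% power with 10% dropout, compound symmetry.**
- First row: 15.70×0.550/0.225²/0.9 = 189.5 for the four-visit mean; 15.70×0.440/0.3²/0.9 = 85.3 for the adjusted mean.
- Second row: 106.6 and 15.70×0.440/0.4²/0.9 = 48.0.

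**The case against.** **The contrast and the baseline parametrisation can be left to the SAP.** This stands in part. The proposed analysis is one form of the planned mixed model, and nothing in 12.2 or 12.3.1 forbids it. But the protocol itself fixes the hypothesis, the four outcome time points and a power claim, and those are what fail to line up.

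**The plan may not mean a four-visit mean.** This also stands. The before-and-after wording in the synopsis and 12.1 leaves room for a treatment-by-time test, in which visit 2 would act as reference. The 2.2 does not apply to that reading. With completers that test has 51% or 78% power in the first two rows of the table, below 80% in both.

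**The ratio is only 1.25 if 0.3 is the four-visit difference.** The 1.25 (0.550/0.440) applies 0.3 to both contrasts, which implies two different true effects. For a single sustained effect the ratio stays 2.22 (106.6 against 48.0).

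**A reader might infer that 116 is too small.** The documents do not support that. Three equally correlated measurements reproduce it, and there are three post-induction visits. A shortfall appears only when an effect of 0.3 at visits 3 to 5 is paired with a test that includes visit 2, or with the 3-df test. Nor is 116 good evidence for four measurements. Four can reach 116.0 with 10% lost before the first sample and again at each interval, but that leaves 0.9⁴ = 0.656 at visit 5. A loss of about 34% does not fit the 10% over time in 12.5 or the 10% ceiling on missing data in 12.4.

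**The visit 3-5 mean is not always best.** This is correct. Drug administration ends with surgery (8.1), so a transient effect is possible. For an effect at visit 3 only, the interaction test has 51% and the adjusted mean 19%.

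**Conclusion.** The concern holds as a loss of efficiency and an unclear power statement. Visit 2 is counted as an outcome, cannot carry a drug effect and is not used as a baseline. If the test is the four-visit main effect, it needs about 2.2 times the patients of the baseline-adjusted visit 3-5 mean under compound symmetry at 0.4, and about 1.2 to 1.6 times under the other structures tried. With 0.3 SD at each later visit, power is about 59% against 90%; if 0.3 is the four-visit difference, the stated 80% is met at 83%.

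These figures rest on normal theory, equal variances and an equal effect at visits 3 to 5. Section 12.5 says that numerical CTC data could not be used for sizing, so they are illustrative for a cell count.

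Bias should not be inferred: every reading is a valid randomised comparison. Nor is there a demonstrated error in 116. That number fits three measurements, hence the post-induction visits, better than the four time points of 12.2 read with 6.2. The change should be made, but it does not call the trial's validity into question.

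**What to change.** In 12.2 and 12.3.1, treat visit 2 CTC as baseline, either as a covariate or by constraining the arms to be equal at visit 2 in the planned mixed model. Define the primary contrast as the between-arm difference in mean CTC over visits 3, 4 and 5. Keep treatment-by-time as a secondary test, because it has more power for an effect confined to one visit.

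In 12.5, state how many measurements, which contrast and which attrition pattern the 0.3 and the 116 refer to, and give the power for the primary contrast as defined. If 0.3 SD applies to the visit 3-5 mean, 116 per group gives about 80% unadjusted and about 90% adjusted under the assumptions above.

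The cost is a protocol amendment, which section 13 requires to be submitted to the ethics committee and Swissmedic, covering wording and one power statement. The primary test would have less power than the interaction test if the effect is transient. No new samples or patients are needed, since visit 2 CTC is already scheduled for everyone.

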12.3 Planned Analyses

All primary and secondary analyses will be performed following an *intention-to-treat* (ITT) model. This analysis will be subsequently compared to a *per-protocol* analysis to assess the impact of patients who were not treated as randomized. Results will be reported as OR, 95% confidence intervals and their associated p-values. A p-value <0.05 will be considered statistically significant.

Data analyses will be performed after enrolment of the last patient and completion of the study. No interim analyses are planned.

12.3.1 Primary Analyses

The primary endpoint, i.e. blood CTC levels, is a continuous variable. In our study, 2 independent variables may interact with CTC levels: a time factor, which results from repeated measurements over time (i.e. within-subjects factor) and an intervention factor, which is the anesthesia regimen (between subjects factor). Thus, our primary analysis will be performed using a linear mixed model with random effects matrix to account for within-subjects correlated observations as indicated for longitudinal data analysis.

12.3.2 Secondary Analyses

Since most reports refer to CTC levels as a binary outcome (i.e. positive *versus* negative endpoint using a cut-off value of ≥ 5 CTC/7.5ml blood), data transformation from a continuous into a binary variable will be performed using the same cut-off value as described previously. This new data set will be analyzed using a logistic regression mixed model with random effects matrix.

Provided our sample size is large enough, adequate randomization is likely to reduce imbalance in baseline characteristics between groups. However, further exploratory analyses will be performed whenever there is a need to control for residual confounding.

12.3.3 Interim Analyses

No interim analyses are planned.

12.4 Handling of Missing Data

Longitudinal data analyses are likely to suffer from error and bias due to missing or incomplete data. In the case of dropouts or incomplete dataset, it remains thus essential to collect a maximal amount of information to determine the nature of missing data (data missing completely at random (MCAR), data missing at random (MAR) or data missing not at random (MNAR)). In case of missing randomness we will consider using multiple imputation for analyses where complete data are needed (linear mixed models can deal with missing data without need for imputation), which is considered superior to a *complete case analysis* (assuming that all data are MCAR or MAR) or a *last observation carried forward* analysis.

In our trial, missing data is not expected to exceed 10% for any variable. This trial will be conducted in a university hospital where clinical research is common practice (trained study nurses, research-orientated infrastructure and care, high standards of quality control). Considerable efforts will be made to ensure high protocol compliance (postoperative medication using a predefined schema provided by the electronic patient database; regular meetings with the anesthesia team to identify potential enrolment or organizational issues).

12.5 Determination of Sample Size

Sample size calculation was performed using a method accounting for a longitudinal design with 2 groups, which allows for repeated measurements and subject attrition. Since most studies investigating perioperative CTC only provide positivity rates rather than numerical levels, we were not able to use these data to estimate our sample size. Therefore, we adopted a conservative approach and assumed that the expected effect size between groups would be small (0.3). This should ensure that our estimation is adequately powered to detect even a small difference between groups. Moreover, we estimated a within-subject correlation over time of 0.4. Thus, to detect a 30% difference between groups, with a power of 80% at a significance level of 5% (two-sided) and assuming a dropout rate of 10% over time, we would need 116 patients in each group (i.e. a total of 232 patients).

